Section 6.6.1 Demographics and Baseline Characteristics	
 1. Added Country as variable, removed Geographic Region as variable 2. Split “Prior nonbiologic JIA therapy” into 2 variables: 
 a. “Prior csDMARDs therapy for JIA” b. “Prior nonbiologic (Non-DMARD) JIA therapy” 3. Split “Number of prior JIA therapy” 
 a. “Number of prior csDMARDs for JIA” b. “Number of nonbiologic (Non-DMARD) JIA therapies” 4. Added row for sulfasalazine 5. Added Biologic JIA therapies “infliximab” and “secukinumab” to abbreviation “c” 6. Added abbreviation “j” to account for csDMARDs therapy category 7. Updated abbreviation “d” 8. Added “including COX-2 inhibitors)” and “systemic glucocorticoids” to abbreviation “d” 9. Removed csDMARDs and MTX from abbreviation “d”
Section 6.9.1 Primary Outcome and Methodology	
 1. Added success criteria language 2. Added posterior mean, variance, and 95% credible interval equations 3. Changed posterior “distribution” to posterior “probability” 4. Updated number “n=80” in baseyan algorithm 5. Added analyse method for JIA ACR30/50/70/100 response (mNRI) 6. Added analyse method for JIA ACR30 response (Bayesian analysis, mNRI)
Section 6.9.5 Sensitivity Analyses	Added new language for sensitivity analysis
Section 6.15 Interim Analyses and Data Monitoring	Added “evaluable” to number of patients needed before stopping for futility Revised entire second paragraph Added “summary of reasons for missing JIA ACR30 data at Week 16”

SAP Version 2 was approved on 03 March 2021.

Revisions since Version 2

Section	Revision
Section 4.1 Primary Objective	Added a section of estimands for Primary Objective
Section 4.2 Secondary Objectives	Added Secondary objectives for the Long-Term Extension (LTE) Period
Section 4.2 Exploratory Objectives	Updated the analyses window for Long-Term Extension (LTE) Period to include Week 264 instead of Week 156
Section 5.1 Summary of Study Design	Added the LTE period description
Figure RHCG.5.1	Updated the schema diagram to include LTE period and added a footnote sentence for superscript “c” as per the current protocol
Table RHCG.6.1 Analysis Populations	Added LTE Safety Population
Section 6.1.2.1 General Considerations for the OLT Period	Updated the baseline definition to include “on or” before
Section 6.1.2.2 General Considerations for the OLE Period	
 Moved “Additional Population Information” from Section 6.1.2.2 to Section 6.1.2.2.1 Added the text “were initially randomized to adalimumab at Week 0 and” under “Additional Population Information”
Section 6.1.2.3 General Considerations for the LTE Period	Added this section to include considerations for the LTE period
Section 6.3.2 Last Observation Carried Forward	Added this under 6.3. Handling of Dropouts or Missing Data to account for the data handling at the component level of JIAACR algorithm
Section 6.5 Patient Disposition	Added the word “LTE” to make the section applicable for the LTE part of the study
Section 6.7 Treatment Compliance	Updated the section for LTE Period Population
Table RHCG.6.3 Number of Injections Prescribed (Assuming adalimumab responders)	Added the column for Long - Term Extension Treatment Period
Section 6.8.2 Concomitant Therapy	Updated the section for LTE Period Population
Table RHCG.6.9 Description and Derivation of Exploratory Efficacy Endpoints	Updated the table to add the exploratory efficacy analyses for LTE Period
Table RHCG.6.10 Description of Analysis Period and Analysis Method of Exploratory Efficacy	Updated the table to add the exploratory efficacy analyses for LTE Period
Section 6.12 Safety Analyses	Updated the whole section to include LTE period details for every subsection.
Section 6.12.1 Extent of Exposure	Added the calculation for The duration of exposure during the LTE Extension
Appendix 1 Algorithm for Determining JIA ACRx Response	Updated as per BARI JIA algorithm Updated “%improvement” to “%change from baseline”
Appendix 2. Algorithm for Calculating Disease Flare	Updated as per BARI Flare algorithm Updated “% improvement” to “% change from baseline”

SAP Version 3 was approved on 20 March 2023.

Revisions since Version 3

Section	Revision
Table RHCG.6.3.Number of Injections Prescribed	Updated the start of LTE period to “104” and number of injections for Ixe OLE to 23 and added a note for number of OLE injection,
Table 6.9.Description and Derivation of Exploratory Efficacy Endpoints :	Added the analysis variable for "Time to inactive/low disease status" for JADAS-27 endpoint.
Table 6.10 Table RHCG.6.10. Description of Analysis Period and Analysis Method of Exploratory Efficacy	Specified the analyses period details for time to inactive/low status Specified missing data handling

4. Study Objectives

4.1. Primary Objective

Table RHCG.4.1. Primary Objective and Endpoint

Objectives	Endpoints
Primary 
 To evaluate the efficacy of ixekizumab in children with JIA subtypes of ERA (including JoAS) and JPsA based on the JIA ACR30 response 	Percentage of patients meeting the JIA ACR30 response criteria at Week 16

Abbreviations: ACR = American College of Rheumatology; ERA = Enthesitis-related Arthritis; JIA = Juvenile Idiopathic Arthritis; JoAS = Juvenile-Onset Ankylosing Spondylitis; JPsA = Juvenile Psoriatic Arthritis.

In compliance with International Conference on Harmonisation (ICH) E9(R1) guidelines, a study should be clear in defining an estimand framework, which includes 4 attributes:

- the population of interest: the patients targeted by the scientific question
- the variable (or endpoint) of evaluation that is obtained for each patient, that is required to address the scientific question
- the population-level summary of the variable, a basis for treatment evaluation, and
- the specification of how to account for intercurrent events to reflect the scientific question of interest.

In particular, for Study RHCG, the estimand is defined by:

- population of interest:** children from 2 to less than 18 years of age, with juvenile idiopathic arthritis (JIA) subtypes of enthesitis-related arthritis (ERA) defined through appropriate inclusion/exclusion criteria to reflect the targeted participant population. Analysis populations are defined in Section 6.1.1.
- variable (or endpoint) of evaluation:** JIA American College of Rheumatology (ACR) 30 response at Week 16 in the ixekizumab arm
- population-level summary:** The primary quantity of interest will be the percentage of patients in the ixekizumab arm meeting the JIA ACR30 response criteria at Week 16. Details are given in Section 6.9.1.
- intercurrent event strategy:** The analysis population will be based on patients who have had the chance to complete the visits. In the estimand framework, for primary variable, the composite estimand strategy will be applied and non-responder imputation will be used to support this strategy. Patients will be considered non-responders for the nonresponder imputation (NRI) analysis if they do not meet the clinical response criteria or have missing clinical response data at the analysis time point of interest. All nonresponders at Week 16 (Visit 8), as well as all patients who discontinue study treatment at any time prior to Week 16 for any reason, will be defined as non-responders for the NRI analysis at Week 16.

4.2. Secondary Objectives

Table RHCG.4.2. Secondary Objective and Endpoint

Objectives	Endpoints
Secondary for the Open Label Treatment (OLT) and Open Label Extension (OLE) Periods	

 • To evaluate the efficacy of ixekizumab in children with JIA subtypes of ERA (including JoAS) and JPsA based on the other clinical responses, disease activity, and physical function measures • To evaluate the efficacy of adalimumab (reference arm) in children with JIA subtypes of ERA (including JoAS) and JPsA based on JIA ACR30 and the other clinical responses, disease activity, and physical function measures 	
The following outcomes will be assessed at each regular study visita:
 
 • Percentage of patients meeting the JIA ACR30/50/70/90/100 response criteria • Changes from baseline in each of the 6 individual components of the JIA ACR core set variables as follows: 
 ○ Number of active joints ○ Number of joints with limited range of motion ○ Physician's Global Assessment of Disease Activity ○ Parent's Global Assessment of Well-Being ○ Physical function as measured by the Childhood Health Assessment Questionnaire (CHAQ) ○ Acute-phase reactant (high-sensitivity C-reactive protein [hsCRP]) and erythrocyte sedimentation rate (ESR) • Change from baseline in Psoriasis Area and Severity Index (PASI) for JPsA patients with at least 3% Body Surface Area (BSA) at baseline • Change from baseline in Leeds Enthesitis Index (LEI) for patients with enthesitis at baseline • Proportion of patients with disease flare (flare defined as worsening of $\geq 30\%$ from baseline in at least 3 of the 6 JIA ACR core set criteria and an improvement of $\geq 30\%$ in no more than 1 of the criteria)

 • To characterize ixekizumab pharmacokinetics (PK) in children with JIA subtypes of ERA (including JoAS) and JPsA 	
 • Trough concentrations of ixekizumab in patients with JIA subtypes of ERA (including JoAS) and JPsA

Objectives	Endpoints

 To evaluate the potential development of anti-ixekizumab antibodies and their impact on the efficacy and safety of ixekizumab in children with JIA subtypes of ERA (including JoAS) and JPsA Describe the safety of ixekizumab in patients with JIA subtypes of ERA (including JoAS) and JPsA 	
 Percentage of patients with anti-ixekizumab antibodies Adverse events (AEs) including serious adverse events (SAEs) Safety parameters including but not limited to infections, injection site reactions, and laboratory data including B-, T-cell, and natural killer (NK)-cell levels, white blood cell (WBC) count, red blood cell (RBC) count, alanine aminotransferase (ALT), aspartate aminotransferase (AST)
Secondary for the Long-Term Extension (LTE) Period	

 To evaluate the long-term safety, tolerability, and efficacy of ixekizumab in children with JIA subtypes of ERA (including JoAS) and JPsA 	
The following outcomes will be assessed at each regular study visit:
 
 AEs including SAEs and adverse events of special interest (AESIs) Safety parameters including but not limited to infections, injection site reactions, and laboratory evaluations (including chemistry and hematology) Permanent and temporary discontinuations of the study intervention Vital signs, growth, and development

Abbreviations: ACR = American College of Rheumatology; ERA = Enthesitis-related Arthritis; JIA = Juvenile Idiopathic Arthritis; JoAS = Juvenile-Onset Ankylosing Spondylitis; JPsA = Juvenile Psoriatic Arthritis.

^a During the OLE period, regular visits and assessments will occur every 3 months (Visits 8, 11, 14, 17, 20, 23, 26, and 29/ETV). Patients will also have monthly treatment visits to the site primarily for dispensation and/or administration of study drug.

4.3. Exploratory Objectives

Table RHCG.4.3. Exploratory Objective and Endpoint

Objectives	Endpoints
Exploratory for the OLT and/or OLE Period	 The content in this cell is completely redacted, appearing as a large red 'CCI' on a black background.

Objectives	Endpoints
CCI	

5. Study Design

[figure not shown]
5.1. Summary of Study Design

Study I1F-MC-RHCG (RHCG) is a multicentre, randomized, open-label study of subcutaneous (SC) ixekizumab, with adalimumab as a reference arm in children from 2 to less than 18 years of age, who are biologic disease-modifying antirheumatic drug- (bDMARD-) naive or inadequate responder (bDMARD-IR) as per investigator's judgement, with JIA subtypes of ERA (including juvenile-onset ankylosing spondylitis [JoAS]) and juvenile psoriatic arthritis (JPsA).

The study consists of 5 periods:

- **Screening Period** (Visit 1) will assess subject eligibility and will occur approximately 7 to 42 days before the Open-Label Treatment (OLT) Period (baseline; Week 0; Visit 2).
- **Open-Label Treatment Period** (OLT) will occur from Week 0 (baseline; Visit 2) to Week 16 (Visit 7). **CCI**
Evaluation of the primary endpoint will occur at Week 16.
- **Open-Label Extension Period** (OLE) will occur from Week 16 (Visit 7) to Week 104 (Visit 29/ Early Termination Visit [ETV]). All patients who were receiving ixekizumab in the OLT period will continue to receive ixekizumab for approximately 88 weeks during the OLE Period. Patients receiving adalimumab during the OLT period who did NOT attain a JIA ACR30 response at Week 16 will be switched to ixekizumab in the OLE period. Patients receiving adalimumab during the OLT period who did attain a JIA ACR30 response at Week 16 will be given the option to switch or not to switch to ixekizumab at any visit during the OLE period. The decision to switch for adalimumab-treated patients who achieved a JIA ACR30 response at Week 16 will be left to the patient/patient's caregiver and investigator. After switching to ixekizumab, the patients will not have the option to resume adalimumab treatment during the remainder of the trial participation.
- **Long-Term Extension Period** (LTE): Participants who complete the OLT and OLE periods will be participating in the LTE period of this study which will occur from Week 104 (Visit 29) to Week 264 (Visit 69/ ETV). All participants entering the LTE portion of the study period will receive weight-based ixekizumab at Week 104. Participants who were previously assigned to adalimumab will be switched to ixekizumab as described in Section 7.1 Treatments Administered of the protocol. If a participant previously assigned to adalimumab does not want to switch to ixekizumab in the LTE period of the study, the patient should initiate the ETV process at Week 104.
- **Post-Treatment Follow-Up Period** (PTFU) is for safety monitoring after treatment discontinuation for any subject receiving at least 1 dose of study drug. Participants who have received at least 1 dose of study drug should enter the PTFU period for a minimum of 12 weeks after the last treatment period visit (Week 104) or ETV their last regularly scheduled visits (or the date of their ETV).

Figure RHCG.5.1 illustrates the study design for the main protocol.

Abbreviations: ACR = American College of Rheumatology; bDMARD = biologic disease-modifying antirheumatic drug; bDMARD-IR = inadequate response to biologic disease-modifying antirheumatic drug; ERA = enthesitis-related arthritis; ETV = early termination visit; JIA = juvenile idiopathic arthritis; JPsA = Juvenile Psoriatic Arthritis; LV = last visit; OLE = open-label extension; PTFU = post-treatment follow-up period; OLT = open-label treatment; Q2W = every other week; Q4W = every 4 weeks; TV = treatment visit; Tx = treatment x; V = visit; W = week.

- a Patients who are bDMARD-naïve will be randomized to ixekizumab or adalimumab in a 1:1 ratio. At least 20 patients will be randomized to ixekizumab and 20 patients to adalimumab. Randomization will be stratified based on the category of JIA (ERA or JPsA). The remaining patients (approximately 60 patients) who are bDMARD-naïve or bDMARD-IR will be assigned to ixekizumab.
- b Patients receiving adalimumab during the OLT period who did NOT attain a JIA ACR30 response at Week 16 will be switched to ixekizumab in the OLE period. Patients receiving adalimumab during the OLT period who did attain a JIA ACR30 response at Week 16 will be given the option to switch or not to switch to ixekizumab in the OLE period.
- c Regular visits will occur every 3 months, but patients will have monthly treatment visits to the site primarily for injection purposes. Participants who are treated with adalimumab through Week 104 may decide not to switch to ixekizumab at Week 104 and enter the PTFU period.

Figure RHCG.5.1. Illustration of study design for Study I1F-MC-RHCG.

5.2. Determination of Sample Size

The Bayesian methodology results in a posterior distribution which rigorously quantifies the uncertainty around the estimate of the JIA ACR30 response. The primary objective of this study is to detect a JIA ACR30 response rate of at least 50% for ixekizumab-treated patients at Week 16.

A sample size of at least 80 patients assigned to ixekizumab has been shown via simulation to have reasonable operating characteristics as follows:

- a study success rate greater than 80% if the true JIA ACR30 response is at 60%
- a false-positive rate of less than 1% if the true JIA ACR30 response is placebo-like at 35%

These rates are derived from the Bayesian decision criterion but are similar to a traditional power calculation.

Overall, approximately 100 patients will be assigned to therapy in this study: 40 will be randomized, 20 to ixekizumab and 20 to adalimumab. The remaining 60 will be assigned to ixekizumab.

The above sample size and power estimates are based on Fixed and Adaptive Clinical Trials Simulator version 6.0 (FACTSTM).

5.3. Method of Assignment to Treatment

Patients who meet all criteria for enrolment will be randomized or assigned, as appropriate, to treatment at Visit 2. **CC1**

At least 20 patients will be randomized to ixekizumab and 20 patients to adalimumab. Randomization will be stratified based on the category of JIA (ERA or JPsA). The remaining patients (approximately 60 patients) who are bDMARD-naïve or bDMARD-IR will be assigned to ixekizumab. In practice, this will be accomplished by randomizing the first 40 bDMARD-naïve patients entering the study according to the ratio and stratification described above, with all the subsequent bDMARD-naïve patients being assigned to ixekizumab. A listing of patient randomization for the Intent to Treat population by site will be provided.

Assignment to treatment groups will be determined by a computer-generated random sequence using an interactive web-response system (IWRS). The IWRS will be used to assign cartons containing investigational product to each patient. Site personnel will confirm that they have located the correct cartons by entering a confirmation number found on the cartons into the IWRS before dispensing to patients.

6. A Priori Statistical Methods

6.1. General Considerations

Statistical analysis of this study will be the responsibility of Eli Lilly and Company (hereafter Lilly). The statistical analyses will be performed using SAS® Version 9.2 or higher. Not all displays described in this SAP will necessarily be included in the clinical study report (CSR). Any display described in this SAP and not provided in the CSR would be available upon request. Not all displays will necessarily be created as a “static” display. Some may be incorporated into interactive display tools instead of or in addition to a static display. Any display created interactively will be included in the CSR if deemed relevant to the discussion.

Bayesian analysis will be used as the primary analysis method for the primary endpoint, JIA ACR30 at Week 16. The posterior probability distribution of JIA ACR30 response rate at Week 16 will be summarized and the conclusion will be made based on the prespecified success criteria. If the study is not stopped for futility, the posterior probability of the Week 16 JIA ACR30 response rate exceeding 50% will be calculated, and the study objective will be successfully met (i.e., a positive study) if this posterior probability is at least 80%.

Continuous data will be summarized in terms of the number of observations, mean, standard deviation (SD), minimum, median, and maximum. The minimum and maximum will be reported to the same number of decimal places as the raw data recorded in the database. The mean and median will be reported to 1 more decimal place than the raw data recorded in the database. The SD will be reported to 2 more decimal places than the raw data recorded in the database. In general, the maximum number of decimal places reported shall be 4 for any summary statistic.

Categorical data will be summarized in terms of the number of patients in the analysis population, the number of patients providing data at the relevant time point, frequency counts, and the percentages corresponding to the appropriate method. Percentages will be presented to 1 decimal place. Percentages will not be presented for zero counts. For condition/event that is gender-specific (as defined by the Medical Dictionary for Regulatory Activities [MedDRA]), the denominator and computation of the percentage will include only patients from the given gender. All confidence intervals (CIs) will be 2-sided with a 95% level of confidence, unless otherwise specified.

All efficacy and safety data collected will be summarized using descriptive statistics without any inferential statistics.

6.1.1. Populations for Analyses

For analysis purposes, populations are defined based on the different treatment period in [Table RHCG.6.1](#). A disposition of the study analysis population and a listing of the analysis population will be provided as well.

Table RHCG.6.1. Analysis Populations

Population	Period	Description
Enrolled		All patients who sign informed consent.
ITT population	OLT	All patients, even if the participant does not take the assigned treatment, does not receive the correct treatment, or otherwise does not follow the protocol. Unless otherwise specified, efficacy and health outcomes analyses will be conducted on the ITT Population during the OLT period. Patients will be analyzed according to the treatment to which they were assigned.
OLE period population	OLE	All patients who receive at least 1 dose of either treatment in OLE.
OLE period adalimumab switchers (switchers)	OLE	Patients initially randomized to adalimumab who switch to ixekizumab in the OLE period
OLT safety population	OLT	All patients who received at least 1 dose of either treatment product in OLT.
LTE safety population	LTE	All participants who received at least 1 dose of ixekizumab in the LTE period
PTFU period population	PTFU	Safety analyses for the Post-Treatment Follow-Up Period will be conducted on the Post-Treatment Follow-Up Period population, defined as all randomized patients who received at least 1 dose of study treatment at any time during the study period, and have entered the Post-Treatment Follow-Up Period. Patients will be analyzed according to the treatment in which they were assigned.

Abbreviations: ITT = Intend-To-Treat; OLE = Open-Label Extension; OLT = Open-Label Treatment; LTE = Long-Term Extension; PTFU = Post-Treatment Follow-Up.

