3.1. Study Rationale

This study is part of the European Paediatric Investigation Plan (PIP), EMEA-001050-PIP02-18- M01, with the aim to evaluate the efficacy, safety, tolerability, and pharmacokinetics (PK) of ixekizumab when administered to pediatric patients with juvenile idiopathic arthritis (JIA) categories of enthesitis-related arthritis (ERA) (including juvenile onset ankylosing spondylitis [JoAS]) and juvenile psoriatic arthritis (JPsA).

The study will include participants who are naive to biologic disease-modifying antirheumatic drugs (bDMARD-naive) and participants with an inadequate response (IR) or intolerance to treatment with at least one bDMARD (bDMARD-IR). The inclusion of bDMARD-naive and bDMARD-IR patients in this study is based on the unmet needs in both ERA and JPsA subsets of JIA. Adalimumab will serve as a reference arm in bDMARD-naive patients, allowing for a descriptive assessment in the same study as in bDMARD-naive patients on ixekizumab, thus providing assay sensitivity and context for the efficacy data.

The rationale for the long-term extension (LTE) period is to evaluate the long-term safety, tolerability, and efficacy of ixekizumab when administered to pediatric patients with JIA categories of ERA (including JoAS) and JPsA. In addition to the established safety profile for adult psoriasis, psoriatic arthritis, and axial spondyloarthritis, further assessments for the safety, tolerability, and efficacy data from this study are intended to establish a better understanding of the long-term benefit-risk relationship for ixekizumab in pediatric patients with ERA and JPsA.

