5.2. Number of Participants

At least 100 participants from 2 to less than 18 years of age with a diagnosis of JIA categories of ERA and JPsA are planned to enter the OLT period.

- For participants who are bDMARD-naïve, at least 20 participants will be randomized to ixekizumab and at least 20 participants will be randomized to adalimumab. Randomization will be stratified based on the category of JIA (ERA or JPsA).
- The remaining participants (approximately 60 participants) who are either bDMARD-naïve or bDMARD-IR will be assigned to ixekizumab.

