Participants that do not achieve JIA ACR 30 response at Week 16 while on adalimumab, will be switched to ixekizumab without a washout period, due to a high need for treatment change/escalation. Evidence from studies in adult participants with IBD or RA suggests no significant safety risk is associated with direct switching between different monoclonal antibodies (Smolen et al. 2016; Mahagna and Ben-Horin 2019). To decrease any potential safety risk in switching participants, the minimum required period between the last adalimumab and first ixekizumab dose will be 2 weeks, and no higher starting dose of ixekizumab will be applied (van der Heijde et al. 2018).

The OLE period allows for long-term evaluation of safety and durability of efficacy in participants who receive ixekizumab. The PTFU will allow for continued safety monitoring after the last dose.

The open-label Bayesian approach is considered methodologically acceptable. The inclusion of adalimumab reference arm, with 1:1 randomization of bDMARD-naive participants to either ixekizumab or adalimumab, will allow for descriptive comparative statistics, thus providing assay sensitivity and context for ixekizumab efficacy data.

An active adalimumab reference arm was used before in the Phase 3 randomized placebo-controlled trials of ixekizumab in bDMARD-naive adult participants with PsA and axSpA (Mease et al. 2017; van der Heijde et al. 2018).

The inclusion of bDMARD-IR participants is driven by the unmet need in participants who had primary or secondary failure or intolerance to bDMARD therapy, including adalimumab.

The long-term open-label extension period allows participants with JIA to receive treatment with ixekizumab for an extended time and provides for collection of longer-term safety, tolerability, and efficacy data for ixekizumab in JIA subtypes of ERA and JPsA.

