6.5. Patient Disposition

The number of patients along with, ITT, OLE, LTE Safety, OLE switcher, and PTFU populations will be summarized, and a listing of disposition will be summarized.

An overview of patient disposition will be summarized by each treatment period using the appropriate populations.

The following patient disposition summaries will be provided (details of the analysis populations can be found in Section 5.1):

- The number and percentage of patients completing Week 16 of the OLT Period on initially assigned treatment and the number and percentage of patients discontinuing on/prior to Week 16 of the OLT Period, by treatment group and primary reason for discontinuation (Analysis population: ITT Population).
- The number and percentage of Switchers completing the OLE Period or prematurely discontinuing from the OLE Period after Week 16, and primary reason for discontinuation (Analysis population: Switcher Population).
- The number and percentage of patients completing the OLE Period and the number and percentage of patients discontinuing from the OLE Period, by treatment group and primary reason for discontinuation, including classified as Switcher during OLE Period (Analysis population: OLE Period Population).
- The number and percentage of patients completing the LTE Period and the number and percentage of patients discontinuing from the LTE Period, by treatment group and primary reason for discontinuation (Analysis population: LTE Safety Population).

- The number and percentage of patients completing the PTFU Period and the number and percentage of patients discontinuing from the PTFU Period, by treatment group and primary reason for discontinuation (Analysis population: PTFU Period Population).

A by-patient listing will also be provided to include the following information:

- Patient disposition during each period, including the date of randomization at Visit 2, the date of first and last dose on initially assigned treatment during the OLT Period, date/reason of initiation of switch to ixekizumab if any, the date of completion or discontinuation of study treatment, the primary reason for discontinuation of study treatment if applicable and date of study discontinuation, and the time to discontinuation (Analysis population: ITT).

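### No readable SAP summary is defined by randomized status: the 1:1 bDMARD-naive comparison is not planned at baseline and is not guaranteed for JIA ACR

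*SAP*

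**What the plan says.** **Purpose of the randomization.** Protocol 5.4 says that the adalimumab arm, "with 1:1 randomization of bDMARD-naive participants to either ixekizumab or adalimumab, will allow for descriptive comparative statistics", and derives assay sensitivity and context from that. Protocol 3.1 describes the purpose as a contrast among naive patients: "allowing for a descriptive assessment in the same study as in bDMARD-naive patients on ixekizumab".

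**Allocation.** Protocol 5.2 sets minimum numbers: "at least 20 participants will be randomized to ixekizumab and at least 20 participants will be randomized to adalimumab". SAP 5.2 gives the planning figures: "40 will be randomized, 20 to ixekizumab and 20 to adalimumab. The remaining 60 will be assigned to ixekizumab". SAP 5.3 (and Protocol 7.2) randomizes the first 40 naive patients, "with all the subsequent bDMARD-naïve patients being assigned to ixekizumab". The remaining 60 or so may be naive or bDMARD-IR, and neither document fixes the split.

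**Populations and summaries.** In SAP Table RHCG.6.1 the efficacy population for the open-label treatment (OLT) period is ITT, with the rule "Patients will be analyzed according to the treatment to which they were assigned". SAP 6.6.1 summarizes baseline for the ITT, OLE and Switcher populations. The readable efficacy tables (RHCG.6.6, 6.8 and 6.10) use those populations or disease-feature subsets of them. The word randomized does appear in the definitions of the switchers and of the post-treatment follow-up safety population, but neither sets the two randomized arms side by side for OLT efficacy or baseline.

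**Near substitutes.**
- Table RHCG.6.2 summarizes prior biologic use (never or ever) in the ITT population and marks it as a subgroup. SAP 6.13 analyses such subgroups for JIA ACR30/50/70/90/100.
- The protocol synopsis promises descriptive summaries by treatment assignment and by bDMARD experience.
- SAP 5.3 adds: "A listing of patient randomization for the Intent to Treat population by site will be provided". SAP 6.5 adds a by-patient listing: "Patient disposition during each period, including the date of randomization at Visit 2". Patient characteristics and the primary endpoint are also listed.

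Exploratory Tables RHCG.4.3, 6.11 and 6.12 and parts of SAP 5.1 and 5.3 are redacted, so this point covers the readable text only.

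**The concern.** The protocol justifies randomizing about 40 children by the comparison that randomization allows. The default display does not show that comparison. It puts a wholly randomized, wholly naive adalimumab column beside an ixekizumab column in which about one patient in four was randomized. A difference between the columns could reflect the drugs, the share of inadequate responders, or the later enrolment of patients who had no concurrent adalimumab group.

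Restricting to patients who never used a biologic removes the inadequate responders. It does not remove the time element, because every naive patient after the 40th goes to ixekizumab. With no baseline summary for either the subgroup or the randomized cohort, a reader of the summary tables cannot see whether the compared groups were alike at entry. What is at stake is the interpretation of the reference arm, not the trial's success criterion.

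**Working it through.** **1. The plan's own figure, to fix what is not in question.** With a Beta(0.5, 0.5) prior and n = 80, the posterior probability that the rate exceeds 50% is 0.749 at 43 responders and 0.814 at 44. Success therefore needs at least 44 responders, that is, fewer than 37 nonresponders, as SAP 6.15.1 states. The exact binomial probability of success is 84.8% at a true rate of 60% and 0.02% at 35%. Both agree with SAP 5.2 (above 80%, below 1%). This rule uses all ixekizumab patients and does not involve adalimumab.

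**2. Composition of the planned columns.** Inputs: 20 randomized to each arm and 60 assigned to ixekizumab (SAP 5.2). Let m be the number of naive patients among the 60. The documents do not give m, so its range is shown. The value m = 60 is only a bound, since Protocol 3.1 says that bDMARD-IR participants will be included.

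- Randomized share of the ITT ixekizumab column: 20/80 = 25%. For adalimumab it is 100%.
- IR share of the ITT ixekizumab column: (60 − m)/80.
- Never-used-biologic ixekizumab group: n = 20 + m, with randomized share 20/(20 + m).

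| m | IR share, ITT ixekizumab | Never-used n | Randomized share of never-used |
|---|---|---|---|
| 0 | 75% | 20 | 100% |
| 20 | 50% | 40 | 50% |
| 40 | 25% | 60 | 33% |
| 60 | 0% | 80 | 25% |

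The subgroup coincides with the randomized cohort only at m = 0.

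**3. How far case mix could move the ITT column (illustration).** The only naive and IR rates in the documents are adult, from separate trials and on other endpoints (Protocol 3.2). In PsA, ACR20/50/70 was 58/40/23% in naive and 53/35/22% in TNF-IR patients, giving gaps of 5, 5 and 1 points. In radiographic axSpA, ASAS40 was 48% and 25%, a gap of 23. Shift against the randomized ixekizumab arm = gap × IR share, for m = 0, 20, 40, 60:

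- gap 5: 3.8, 2.5, 1.3, 0 points
- gap 23: 17.3, 11.5, 5.8, 0 points

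These figures show scale and do not estimate the effect in this trial.

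**4. How far calendar time could move the never-used subgroup.** Suppose later naive patients differ by 10 points from the randomized ones (an assumption; the documents give no figure). Shift = 10 × m/(20 + m) = 0, 5.0, 6.7, 7.5 points for m = 0, 20, 40, 60.

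**5. Precision of a randomized display.**
- Exact 95% intervals for one arm: 12/20 gives 36.1–80.9%; 16/20 gives 56.3–94.3%.
- Half-width for a 20 v 20 difference, 1.96 × √(2p(1 − p)/20): 30.4 points at p = 0.6 and 24.8 at p = 0.8.
- At an assumed rate of 70%, the 20-patient standard error is √(0.21/20) = 10.2 points. For the pooled never-used group, with later patients at 60%, the root-mean-square error is √[(20 × 0.21 + m × 0.24)/(20 + m)² + (0.1m/(20 + m))²] = 9.0, 9.1, 9.2 points for m = 20, 40, 60.

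Under that assumption, the randomized column is no more accurate as an estimate of the ixekizumab rate.

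**The case against.** The strongest reply is that the plan already supplies most of what is wanted. The ITT baseline table reports prior biologic use, so the naive/IR mix of each column can be read directly. The synopsis promises summaries by bDMARD experience. SAP 6.13 gives JIA ACR for the never-used subgroup; that section does not itself say by treatment, but the ITT grouping rule and Protocol 10.3.7.1 imply it. The adalimumab ITT column is already the randomized arm. Listings may allow the cohort to be rebuilt, SAP 6.13 permits further subgroups, and SAP 6.1 makes displays left out of the CSR available on request. All comparisons are descriptive, Protocol 5.4 names no specific table, and step 5 shows no gain in accuracy.

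Most of this stands, and it rules out two stronger readings. A reader might infer that no naive comparison is planned, or that the enrolment mix is hidden. The documents support neither.

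It does not close the gap. None of these summaries is split by randomized status. The subgroup is the randomized comparison only if no naive patient is assigned after the 40th, which the plan does not require, and SAP 6.6.1 plans no baseline summary for it. Listings and permission to add analyses are not prespecified summaries. The accuracy argument concerns the error in one arm's rate under an assumed drift; the case for the randomized display is that both arms come from the same allocation over the same period.

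**Conclusion.** The point holds for the readable text, as a modest one. The randomized comparison on which Protocol 5.4 relies is not planned for baseline and is not guaranteed for JIA ACR. Only about 25% of the ITT ixekizumab column is randomized. In the never-used subgroup the share is between 25% and 100%, depending on m, which is not stated. The point shifts in steps 3 and 4 rest on adult cross-trial gaps or on an assumed drift and should not be quoted as expected bias.

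A reader might go further and infer that the primary result is compromised. It is not: the decision rule is single-arm, its stated operating characteristics are reproduced, and it does not depend on the adalimumab comparison. Nor do the documents show that the randomized contrast would be lost, since it may be recoverable from listings. What is missing is a prespecified summary of it. The redacted exploratory tables could contain one, and this cannot be checked.

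**What to change.** Add to Table RHCG.6.1 a *Randomized cohort*: all bDMARD-naive participants randomized in IWRS, by randomized arm. For this cohort, prespecify:

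1. the Table RHCG.6.2 baseline summary; and
2. in Table RHCG.6.8, Week 16 JIA ACR30 with NRI and a 95% interval per arm.

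Label both as descriptive, consistent with Protocol 10.3.1 and SAP 6.1. Footnote the pooled ixekizumab ITT column to say that it is not a randomized comparison with adalimumab, and give the actual number assigned without randomization.

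The cost is one flag from existing IWRS data, one baseline table, one efficacy row and a footnote. The downside is wide intervals that cannot support a comparative claim. The sample size, primary analysis and decision rule do not change.
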